COMIRB Protocol

COLORADO MULTIPLE INSTITUTIONAL REVIEW BOARD
[name] [contact] [contact]

Project Title: Evaluation of speech-in-noise performance in cochlear implant recipients using either a conventional hearing aid or a CROS device on the contralateral ear

Version: January 30, 2019

Principal Investigator: [name]

COMIRB #: 18-1101

I. Hypotheses and Specific Aims:

Speech understanding in noise remains the greatest challenge for individuals utilizing cochlear implants, particularly when the speech of interest originates from the side of the head opposite to the implant. Recent advances in hearing technology allow for an individual to either use a conventional hearing aid or a Contralateral Routing of Signal (CROS) device on the non-implanted ear. Differences in speech understanding may result depending on the specific device chosen by an individual, and these differences may be measureable through speech discrimination measurement protocols.

Hypotheses:

1. Performance on a speech perception task will vary based on the type of amplification device a listener uses on the ear contralateral to the cochlear implant
2. As the originating locations of the speech and noise are varied, the amount of benefit seen by specific device configurations (cochlear implant + hearing aid or cochlear implant + CROS) will also vary.
3. Perceived listening effort will vary as device and speech/noise original locations are varied

Specific Aims:

1. Quantify the changes in speech in noise perception for adults using a cochlear implant in one ear as the device on the contralateral ear is varied.
2. Quantify the changes in speech in noise perception for adults using a cochlear implant in one ear as the originating locations of the speech and noise are varied.
3. Quantify the self-reported amount of listening effort perceived by a listener when listening to speech in noise for a variety of device and speech/noise location configurations.

Consented subjects will fill out a case history form and participate in various speech and hearing tests under 7 conditions which will provide data on which device condition produced the best speech perception in noise results.

This study intends to determine whether or not a CROS device improves speech perception in noise when the source of the speech of interest originates from the side of the head opposite to the implant.

II. Background and Significance:

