Study data will be collected and managed using REDCap (Research Electronic Data Capture). REDCap is a secure web application designed to support data capture for research studies, providing user-friendly web-based case report forms, real-time data entry validation (e.g. for data types and range checks), audit trails and a de-identified data export mechanism to common statistical packages (SPSS, SAS, Stata, R/S-Plus). The system was developed by a multi-institutional consortium which includes University of Colorado–Denver and was initiated at Vanderbilt University. The database is hosted at the University of Colorado–Denver Development and Informatics Service Center (DISC), which will be used as a central location for data processing and management. REDCap data collection projects rely on a thorough study-specific data dictionary defined in an iterative self-documenting process by all members of the research team with planning assistance from the DISC. This iterative development and testing process results in a well-planned data collection strategy for individual studies. REDCap also includes a powerful tool for building and managing online surveys. The research team can create and design surveys in a web browser and engage potential respondents using a variety of notification methods. REDCap is flexible enough to be used for a variety of types of research and provides an intuitive user interface for database and survey design and data entry.

E. Potential Scientific Problems:

There are no known scientific problems at this time.

F. Statistical Analysis Plan

Sample Size Estimate:

The standard deviation for speech reception thresholds (SRTs) for individuals with cochlear implants was used for an estimate of within group variation. This value, obtained from a similar analysis of an Advanced Bionics device versus a Cochlear Corporation device (Gifford & Revit 2010), is estimated to be 3.2 dB.

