This study will utilize a modified eight-period crossover design for the two treatments, where 4 sequences will be used for each hearing device. A power analysis was conducted using simulations to detect a difference in speech reception thresholds of 2 dB between two groups at an alpha level of 0.05. A sample size of 14 subjects total provides 90% power to detect a difference in speech reception thresholds of 2 dB. To assess the accuracy of these simulations, other non-simulated power analyses showed similar results, even though these methods do not directly apply this study's design. This change of 2 dB is a clinically meaningful difference that we consider a realistic expectation of the intervention, the CROS device, in this study. Although no attrition is expected, we will recruit up to 50 subjects which will give more power so that the interactions can be estimated more accurately.

Statistical Analysis Plan:

Statistical analysis will be carried out using SAS. A linear mixed model will be fit with SAS PROC MIXED using a random subject effect. The primary outcome, speech reception threshold (dB), will be regressed on the main effect of treatment (CROS hearing device vs. conventional hearing aid), signal location (directly to the CI ear vs. opposite), and noise location (directly to the subject's non-CI ear vs. diffuse in the room), as well as the interactions between device type and locations. This method provides valid handling of occasional missing observations. Contrasts will be used within the model to estimate both overall effects and differences in conditions.

G. Summarize Knowledge to be Gained:

This study intends to determine whether or not a conventional hearing aid or a CROS device utilized on the ear contralateral to cochlear implantation improve speech perception in noise when the source of the speech of interest originates from the side of the head opposite to the cochlear implant.

H. References:

Bronkhorst, A. W., & Plomp, R. (1988). The effect of head-induced interaural time and level differences on speech intelligibility in noise. *The Journal of the Acoustical Society of America*, 83(4), 1508-1516.

Cherry, E. C. (1953). Some experiments on the recognition of speech, with one and with two ears. *The Journal of the acoustical society of America*, 25(5), 975-979.

Ching, T. Y., Incerti, P., & Hill, M. (2004). Binaural benefits for adults who use hearing aids and cochlear implants in opposite ears. *Ear and hearing*, 25(1), 9-21.

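### The SAP names no primary device contrast and no multiplicity rule, so its averaged device effect and open list of condition contrasts do not settle the question about speech opposite the implant

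*Combined protocol and SAP*

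**What the plan says.** Section IV.A gives the primary outcome only as the results of speech-in-noise tests. Section IV.F makes it the speech reception threshold (SRT) in dB and models it with three two-level factors: device (CROS or conventional hearing aid), signal location (CI ear or opposite) and noise location (non-CI ear or diffuse), plus device-by-location interactions. It then states: "Contrasts will be used within the model to estimate both overall effects and differences in conditions". No contrast is ranked first and no adjustment is given.

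The only significance level is in the sample-size text, where simulations were run to "detect a difference in speech reception thresholds of 2 dB between two groups at an alpha level of 0.05". The result is "A sample size of 14 subjects total provides 90% power to detect a difference in speech reception thresholds of 2 dB". The SD "is estimated to be 3.2 dB", and the design is a "modified eight-period crossover design for the two treatments, where 4 sequences will be used for each hearing device".

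The scientific question is narrower than the model's device effect. Section I asks "whether or not a CROS device improves speech perception in noise when the source of the speech of interest originates from the side" away from the implant, and Section IV.G repeats the point for both devices. Hypothesis 2 expects "the amount of benefit seen by specific device configurations" to change with the locations of speech and noise.

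The condition list in Section IV.D has 15 entries: five speech/noise configurations, each with three device states.

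**The concern.** A device effect averaged over locations answers a different question from the one in Section I. If the CROS advantage is confined to speech on the non-CI side, the average shrinks it and the overall test can miss it.

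The condition contrasts could recover it, but they form an open list. With nothing named in advance, a chance difference in one configuration can be reported as the finding, and a reader cannot tell which result the trial was designed to deliver. The stated power also appears to belong to the averaged effect and not to the stated question.

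**Working it through.** **Inputs.** From Section IV.F: difference 2 dB, SD 3.2 dB, alpha 0.05, 14 subjects, up to 50 recruited, eight periods over two devices (read as four observations per device per subject). From Section IV.D: five configurations, three device states. Assumptions: two-sided tests, 3.2 dB taken as the within-subject residual SD, independent residuals with equal variance.

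**1. The plan's own figure.** The SE of a device difference averaged over k observations per device is 3.2 × √(2/(k·n)).
- k=4, n=14: SE = 3.2 × √(2/56) = 0.605. 2/0.605 = 3.31, and Φ(3.31 − 1.96) = 91% (90.5% by noncentral t on 91 df). This matches the stated 90%.
- k=1, n=14: SE = 3.2 × √(2/14) = 1.209. 2/1.209 = 1.65, and power is 38% by the normal formula (33% by paired t on 13 df).

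So the 90% fits a device effect averaged over four observations per device, not a single configuration.

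**2. Chance of at least one false device difference, each contrast at 0.05, no true device effect.** Independent tests give 1 − 0.95^m. Simulation (n=14 and n=50, results within about one percentage point) adds the correlation from shared arms and from the overall contrast.

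| Contrasts tested | m | If independent | Simulated |
|---|---|---|---|
| CROS vs hearing aid, SAP's four cells + overall | 5 | 23% | about 20% |
| CROS vs hearing aid, five configurations + overall | 6 | 26% | about 24% |
| All three device pairs, five configurations | 15 | 54% | 47–48% |
| The same + three overall contrasts | 18 | 60% | about 50% |

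The last two rows need CI-only, which is not a level of the SAP's device factor. The first row follows the model's 2 × 2 location layout. The condition list has no entry for CI-side speech with directional noise, so only three of those cells are actually tested. Three independent contrasts alone give 1 − 0.95³ = 14%.

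**3. Dilution.** Suppose CROS is better by 2 dB in the two configurations with non-CI-side speech and equal elsewhere. Power is by noncentral t.
- Five-configuration average: (2+2+0+0+0)/5 = 0.8 dB. SE = 3.2 × √(2/(5n)) = 0.541 at n=14 and 0.286 at n=50. Power is 31% and 80%.
- Contrast on the two configurations only: 2 dB. SE = 3.2 × √(2/(2n)) = 0.855 and 0.453. Power is 64% and 99%.
- SAP's 2 × 2 layout: (2+2+0+0)/4 = 1.0 dB. SE is 0.605 at n=14, and power is 37%. At n=50 it is 88%.

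**4. Subjects for 90% on the targeted contrast.** Observations per device = 2 × 3.2² × (1.96 + 1.282)² / 2² = 53.8, so 54. With two per subject, that is 54/2 = 27 subjects. A single configuration would need 54, above the planned maximum of 50.

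**The case against.** The contrast sentence speaks of estimating, not testing, and 0.05 appears only in the power statement. A reader might infer that every within-condition contrast will be tested at 0.05, with close to an even chance of a false finding. The documents do not support that. The SAP's device factor has two levels and its location factors have no front-speech level, so the model as written cannot form the 15 pairwise contrasts behind the 47–50% range. That objection stands, and those figures are only an upper scenario.

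It is also fair that the two harms do not fall on the same reading. If the configurations are examined separately, the effect is not lost in an average; if only the average is tested, there is little multiplicity. The model does include interactions, and the SAP justifies recruiting up to 50 subjects by their estimation, so hypothesis 2 is addressed. At 50 subjects the diluted test still has 80% power. But the plan does not say which reading applies, and that is the gap.

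The comparator is also open. Sections I and IV.G ask whether a device improves perception, which can be read as a comparison with CI alone. CROS versus hearing aid is the comparison that the SAP models and powers, which is the reason to prefer it as primary. That choice is not forced.

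**Conclusion.** The point holds as a gap in specification. The plan has no primary contrast and no multiplicity rule, and its power statement fits a location-averaged effect while its question concerns one side.

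Unadjusted testing would give a false-difference rate of about 20% under the SAP's own model and about 24% over the five configurations, rising to about 50% only with CI-only contrasts that the model omits. These rates assume no device effect anywhere. The loss from averaging is large at n=14 (31% against 64%) and smaller at n=50 (80% against 99%). Those figures assume zero effect in the other three configurations and a residual SD of 3.2 dB, which the SAP describes only as within-group variation. An opposite effect in the other configurations would make the dilution worse.

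**What to change.** Before analysis, add to Section IV.F:
- One primary contrast: CROS minus hearing aid in mean SRT with speech at the non-CI side, averaged over conditions 2/3 and 11/12, two-sided 0.05. Its type I error is then 5%.
- The all-location average reported as descriptive.
- Holm adjustment over the remaining device contrasts, including CROS minus CI-only. The model needs a CI-only level for these.
- Power restated for the primary contrast: about 64% at n=14, and about 27 subjects for 90%.

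Two conflicts must be reconciled first. The SAP's directional noise level is at the non-CI ear, while conditions 10–12 put the noise at the CI ear. Condition 10 is labelled as no device where the parallel entries say CI only, and no CI-only contrast should use it until that is settled. The primary contrast does not use condition 10.

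The cost is a few sentences and no new test conditions. The stated 90% at n=14 does not carry over to the primary contrast, so recruitment has to go beyond 14, within the planned maximum of 50. Secondary contrasts will need smaller p-values.
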